8.2.1.1 Pregnancy Tests

The following tests are applicable to female participants only and will be conducted in accordance with the schedules provided in the SoA (Table 3).

• Serum beta-human chorionic gonadotropin (HCG): To be performed for all female participants at Visit 1 except for those who are NOT of childbearing potential as defined in inclusion criterion 12. This test is to be sent to and analyzed at the central laboratory.

- FSH: To be performed at Visit 1 only for female participants < 50 years who have been amenorrhoeic for ≥ 12 months prior to the planned date of randomization to confirm postmenopausal status. This test is to be sent to and analyzed at the central laboratory; all females should be treated as pre-menopausal until results are received from the central laboratory.
- Urine HCG (dipstick): To be performed locally at the study site before each IP administration (starting at Visit 2 through the EOT), and at IPD visits for all female participants except for those who are NOT of childbearing potential as defined in inclusion criterion 12. A positive urine test result must be confirmed with serum beta-HCG.

8.2.1.2 Serology

Hepatitis B surface antigen and hepatitis C antibody tests will be assessed in accordance with the SoA (Table 3); tests are to be performed at the central laboratory.

In case of positive result of hepatitis B surface antigen or hepatitis C virus antibody, additional testing (eg, hepatitis C ribonucleic acid [RNA] polymerase chain reaction test) may be performed.

HIV-1 and HIV-2 antibodies (along with p24 Antigen): To be performed only at screening; test to be performed at the central laboratory.

Instructions for sample collection, processing, storage, and shipment are provided in the laboratory manual.

8.2.2 Physical Examinations

Physical examinations (complete or brief), including height and weight, will be conducted in accordance with the schedule provided in Table 3. Baseline data will be collected at the randomization visit (Visit 2) before administration of the first dose of IP. Any new findings or aggravated existing abnormalities, judged as clinically significant by the Investigator, will be reported as an AE as described in Section 8.3.5.

The complete physical examination will include an assessment of the following: general appearance, skin, head and neck (including eyes/conjunctivitis, ears, nose, mouth, and throat), lymph nodes, abdomen, musculoskeletal (including spine and extremities), cardiovascular, respiratory, and neurological systems.

The brief physical examination will include an assessment of the general appearance, head and neck (including eyes/conjunctivitis, nose), abdomen, cardiovascular, and respiratory system. For the brief physical examination, only information on whether the assessment was performed or not is to be recorded.

Weight measurements will be performed in light clothing and without shoes and will be recorded in kilograms.

8.2.3 Vital Signs

Pre-dose vital signs (pulse rate, blood pressure, respiratory rate, and body temperature) will be assessed in accordance with the SoA (Table 3).

It is recommended that vital signs are assessed before any interventional study procedures (blood test collection, IP administration).

Body temperature will be measured in Celsius in accordance with local standards.

Blood pressure and pulse measurements will be assessed while sitting with a completely automated device. Manual techniques will be used only if an automated device is not available. The pulse rate and blood pressure will be measured after the participant has been resting for at least 5 minutes in a quiet setting without distractions (eg, television, cell phones). The pulse rate should be obtained before blood pressure.

The respiration rate will be obtained after the participant has been resting for at least 5 minutes, by counting the number of breaths (how many times the chest rises) for 1 minute.

8.2.4 Electrocardiograms

Single 12-lead electrocardiogram (ECG) will be obtained locally during screening (Table 3) using an ECG machine that automatically calculates the heart rate and measures PR, QRS, and QT intervals. The ECG results will be interpreted locally.

The Investigator or authorized delegate will be responsible for the overall interpretation and determination of clinical significance of any potential ECG findings. The ECG printouts will be signed and dated by the Investigator and stored at the study site. Any findings will be recorded in the eCRF.

ECG will be taken in the supine position, after the participant has been resting for at least 5 minutes. The assessment should be performed before interventions with the participant (eg, IP administration).

8.3 Adverse Events and Serious Adverse Events

The Principal Investigator is responsible for ensuring that all staff involved in the study are familiar with the content of this section.

The definitions of an AE or SAE can be found in Appendix B.

AEs will be reported by the participant (or, when appropriate, by a caregiver, surrogate, or the participant's legally authorized representative).

The Investigator and any designees are responsible for detecting, documenting, and recording events that meet the definition of an AE or SAE. For information on how to follow up AEs refer to Section 8.3.2.

Care will be taken not to introduce bias when detecting AEs and/or SAEs. Open-ended and non-leading verbal questioning of the subject is the preferred method to inquire about AE occurrences.

8.3.1 Time Period and Frequency for Collecting AE and SAE Information

All AEs will be collected starting from Visit 1, throughout the treatment period, and including the follow-up period last contact with participant.

Serious AEs will be recorded from the time the participant signs the ICF, throughout the duration of the study. All SAEs will be recorded and reported to the AstraZeneca representative within 24 hours, as indicated in Appendix B. The Investigator will submit any updated SAE data to the AstraZeneca representative within 24 hours of it being available.

If the Investigator becomes aware of a SAE with a suspected causal relationship to the investigational medicinal product that occurs after the end of the clinical study in a participant treated by him or her, the Investigator shall, without undue delay, report the SAE to the AstraZeneca representative.

8.3.2 Follow-up of AEs and SAEs

After the initial AE/SAE report, the Investigator is required to proactively follow each participant at subsequent visits/contacts. All AEs will be followed until resolution, stabilization, the event is otherwise explained, or the participant is lost to follow-up.

Any AEs that are unresolved at the end of the study (final DBL) will be followed-up by the Investigator for as long as medically indicated, but without further recording in the eCRF. AstraZeneca retains the right to request additional information for any participant with ongoing AE(s)/SAE(s) at the end of the study, if judged necessary.

Adverse Event Variables

The following variables will be collected for each AE:

- AE (verbatim)
- The date when the AE started and stopped
- Maximum intensity

- Whether the AE is serious or not
- Investigator causality rating against the IP (yes or no)
- Action taken with regard to the IP
- AE caused participant's withdrawal from study (yes or no)
- Outcome

In addition, the following variables will be collected for SAEs:

- Description of AE
- Date AE met criteria for SAE
- Date Investigator became aware of SAE
- AE is serious due to (see definition of SAE in Appendix B 2)
- Date of hospitalization
- Date of discharge
- Probable cause of death
- Date of death
- Autopsy performed
- Causality assessment in relation to study procedure(s)
- Causality assessment to other medication

8.3.3 Causality Collection

The Investigator will assess causal relationship between IP and each AE, and answer 'yes' or 'no' to the question 'Do you consider that there is a reasonable possibility that the event may have been caused by the IP?'

For SAEs, causal relationship will also be assessed for other medication and study procedures. Note that for SAEs that could be associated with any study procedure, the causal relationship is implied as 'yes'.

A guide to the interpretation of the causality question is found in Appendix B.

8.3.4 Adverse Events Based on Signs and Symptoms

All AEs spontaneously reported by the participant or care provider or reported in response to the open question from the study site staff: 'Have you had any health problems since the previous visit/you were last asked?', or revealed by observation will be collected and recorded in the eCRF. When collecting AEs, the recording of diagnoses is preferred (when possible) to recording a list of signs and symptoms. However, if a diagnosis is known and there are other

signs or symptoms that are not generally part of the diagnosis, the diagnosis and each sign or symptom will be recorded separately.

8.3.5 Adverse Events Based on Examinations and Tests

The results from the protocol-mandated laboratory tests and vital signs will be summarized in the CSR. Deterioration as compared to baseline in protocol-mandated laboratory values and vital signs should therefore only be reported as AEs if they fulfill any of the SAE criteria, are the reason for discontinuation of treatment with the investigational product, or are considered to be clinically relevant as judged by the Investigator (which may include but not limited to consideration as to whether treatment or non-planned visits were required or other action was taken with the study intervention, eg, drug interruption).

If deterioration in a laboratory value/vital sign is associated with clinical signs and symptoms, the sign or symptom will be reported as an AE and the associated laboratory result/vital sign will be considered as additional information. Wherever possible the reporting Investigator uses the clinical, rather than the laboratory term (eg, anemia versus low hemoglobin value). In the absence of clinical signs or symptoms, clinically relevant deteriorations in non-mandated parameters should be reported as AE(s).

Deterioration of a laboratory value, which is unequivocally due to disease progression, should not be reported as an AE/SAE.

Any new or aggravated clinically relevant abnormal medical finding at a physical examination as compared with the baseline assessment will be reported as an AE unless unequivocally related to the disease under study.

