8.3.6 Disease Under Study

Symptoms of disease under study are those which might be expected to occur as a direct result of AD (eg, erythema, inducation/papulation, lichenification, oozing/crusting, pruritus). Events which are unequivocally due to AD should not be reported as an AE during the study unless they meet SAE criteria or lead to discontinuation of the IP.

8.3.7 **Reporting of Serious Adverse Events**

All SAEs have to be reported, whether or not considered causally related to the IP, or to the study procedure(s). All SAEs will be recorded in the eCRF.

If any SAE occurs in the course of the study, Investigators or other site personnel will inform the appropriate AstraZeneca representatives within one day, ie, immediately but no later than 24 hours of when he or she becomes aware of it. The designated AstraZeneca representative will work with the Investigator to ensure that all the necessary information is provided to the AstraZeneca Patient Safety data entry site within one calendar day of initial receipt for fatal and life-threatening events and within 5 calendar days of initial receipt for all other SAEs.

For fatal or life-threatening AEs where important or relevant information is missing, active follow-up will be undertaken immediately. Investigators or other site personnel will inform AstraZeneca representatives of any follow-up information on a previously reported SAE within one calendar day ie, immediately but no later than 24 hours of when he or she becomes aware of it).

If the electronic data capture system is not available, then the Investigator or other study site staff reports an SAE to the appropriate AstraZeneca representative by telephone.

The AstraZeneca representative will advise the Investigator/study site staff how to proceed.

The reference document for definition of expectedness/listedness is the Investigator's Brochure for benralizumab.

For further guidance on the definition of an SAE, see Appendix B.

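### Protocol Section 8.3.5 bars reporting of disease-related laboratory deterioration even as an SAE, against Sections 8.3.6, 8.3.7 and 8.3.1; the practical gap is narrow and one sentence closes it

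*Protocol*

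**What the plan says.** Section 8.3.5 of the protocol has four paragraphs, of which three bear on laboratory values.

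- The first covers protocol-mandated laboratory tests and vital signs. Deteriorations "should therefore only be reported as AEs if they fulfill any of the SAE criteria", or if they are the reason for stopping IP, or if the investigator judges them clinically relevant.
- The second covers laboratory changes that come with clinical signs or symptoms. In that case "the sign or symptom will be reported as an AE and the associated laboratory result/vital sign will be considered as additional information".
- The third reads: "Deterioration of a laboratory value, which is unequivocally due to disease progression, should not be reported as an AE/SAE". No exception follows.

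Three other sections set the wider rules.

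- Section 8.3.6, on the disease under study, says of events clearly caused by AD that they "should not be reported as an AE during the study unless they meet SAE criteria or lead to discontinuation of the IP".
- Section 8.3.7 says: "All SAEs have to be reported, whether or not considered causally related to the IP, or to the study procedure(s)".
- Section 8.3.1 says: "All SAEs will be recorded and reported to the AstraZeneca representative within 24 hours, as indicated in Appendix B".

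**The concern.** The third paragraph of Section 8.3.5 names SAEs expressly. It therefore switches off, for laboratory values, the exception that Section 8.3.6 preserves for AD events in general. A site that follows the laboratory sentence and a site that follows Sections 8.3.6 and 8.3.7 would handle the same event differently.

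Two things are at stake.

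- **Named safety assessments.** Seriousness and AEs leading to IP discontinuation are listed in the safety objective (Table 5), and Section 9.4.3 plans tables for both. An event withheld under Section 8.3.5 drops out of those tables.
- **The causality question.** Section 8.3.3 asks the investigator whether the IP may have caused each AE. Under the laboratory sentence, the site's view that a change is disease removes the event before that question is put. Section 8.3.7 is written so that attribution to the IP does not decide whether an SAE is reported.

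**Working it through.** No arithmetic applies. The check takes a laboratory deterioration that the investigator attributes unequivocally to AD and runs it through each rule.

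| Situation | 8.3.5, third paragraph | 8.3.5, first paragraph (mandated tests) | 8.3.6 | 8.3.7 and 8.3.1 | Another route |
|---|---|---|---|---|---|
| A. Serious, participant hospitalised | Do not report | Report | Report | Report | Section 8.8 requires hospitalisations after consent to be reported as SAEs |
| B. Accompanied by signs or symptoms that are serious or stop IP | Do not report the laboratory value | Report | Report | Report if serious | 8.3.5, second paragraph: the sign or symptom is the event |
| C. Isolated laboratory change, serious, no hospitalisation | Do not report | Report | Report | Report | None |
| D. Isolated laboratory change, not serious, leads to IP discontinuation | Do not report | Report | Report | Not applicable | None for AE reporting |
| E. Not serious, IP continued | Do not report | Report only if judged clinically relevant | Do not report | Not applicable | None needed |

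Reading down the rows:

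1. In A and B the wording conflicts, but the event still reaches the safety database by another route.
2. In C and D one sentence says do not report, the other applicable rules say report, and no other AE route exists. These two rows are the practical gap.
3. In E the third paragraph agrees with Section 8.3.6. This is the case the sentence can properly cover.

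How often C or D would arise can be judged only roughly. Section 2.1 links two laboratory measures to worse AD. Blood eosinophils are one, but Section 6.3.2 and the footnote to Table 10 redact them from site reports from Visit 2, so sites could seldom apply the sentence to them. Lactate dehydrogenase, described for colonised patients, is the other, and it is not among the safety tests in Table 10. The protocol therefore offers no ready example, which points to few events and possibly none.

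**The case against.** The strongest case on the other side is that the wording does almost no harm.

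- **Serious worsening of AD.** A reader might infer that it can go unreported. The documents do not support that. Section 8.3.6 captures serious clinical worsening, Section 8.8 captures hospitalised flares, and the second paragraph of Section 8.3.5 routes accompanying signs and symptoms to AE reporting.
- **Comparison between arms.** A reader might also infer that missing events could shift the SAE comparison. Nothing supports a count large enough for that, and Section 9.4.3 presents safety descriptively unless the SAP says otherwise.
- **Physical examination.** The last sentence of Section 8.3.5 exempts findings due to the disease, which might look like the same defect. It speaks only of AEs and not of SAEs, so it does not override Section 8.3.7, and it can be read together with Section 8.3.6, which follows directly.
- **The data are kept.** Scheduled safety laboratory tests are run centrally (Section 8.2.1) and summarised with shifts and noteworthy values (Section 9.4.3). The reason for stopping IP is recorded in the eCRF (Section 7.1).
- **Specific over general.** The third paragraph of Section 8.3.5 can be read as a carve-out from the first. Section 8.3.6 gives clinical signs as its examples, so one could argue that it does not reach laboratory values.

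The first three points stand and limit the finding to rows C and D. The fourth stands for the laboratory values, but a tabulated value is not an SAE report: it brings no 24-hour notification and no causality assessment. The fifth leaves the main conflict in place, because Sections 8.3.7 and 8.3.1 cover all SAEs and contain no carve-out for laboratory values or for the disease.

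**Conclusion.** The sentence is wrong as written. It contradicts the first paragraph of its own section for protocol-mandated tests, the exception in Section 8.3.6, and the all-SAE rule in Sections 8.3.7 and 8.3.1. The text at hand does not say which prevails.

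The size is small. The affected events are laboratory deteriorations attributed to AD that are serious without hospitalisation or reportable signs and symptoms, or that lead to IP discontinuation. Few are expected, possibly none. Efficacy, sample size and the between-arm SAE comparison are not called into question.

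The conclusion rests on the text at hand. Appendix B, to which Sections 8.3.1 and 8.3.7 refer, is not included, so whether it settles precedence cannot be checked. Even if it does, Section 8.3 still contradicts itself.

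**What to change.** In the third paragraph of Section 8.3.5, delete the reference to SAE so that the sentence limits AE reporting only, and add the exception that Section 8.3.6 already carries for events that meet SAE criteria or lead to IP discontinuation. Rows C and D then become reportable under every applicable rule, and row E stays exempt as Section 8.3.6 intends. When making the change, check that Appendix B agrees.

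A cross-reference to Section 8.3.6 in the physical-examination sentence would be optional tidying.

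The cost is one clause in one section. It uses wording the protocol already contains and needs no new data, procedure or analysis.

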8.3.6 Disease Under Study

Symptoms of disease under study are those which might be expected to occur as a direct result of AD (eg, erythema, inducation/papulation, lichenification, oozing/crusting, pruritus). Events which are unequivocally due to AD should not be reported as an AE during the study unless they meet SAE criteria or lead to discontinuation of the IP.

8.3.7 **Reporting of Serious Adverse Events**

All SAEs have to be reported, whether or not considered causally related to the IP, or to the study procedure(s). All SAEs will be recorded in the eCRF.

If any SAE occurs in the course of the study, Investigators or other site personnel will inform the appropriate AstraZeneca representatives within one day, ie, immediately but no later than 24 hours of when he or she becomes aware of it. The designated AstraZeneca representative will work with the Investigator to ensure that all the necessary information is provided to the AstraZeneca Patient Safety data entry site within one calendar day of initial receipt for fatal and life-threatening events and within 5 calendar days of initial receipt for all other SAEs.

For fatal or life-threatening AEs where important or relevant information is missing, active follow-up will be undertaken immediately. Investigators or other site personnel will inform AstraZeneca representatives of any follow-up information on a previously reported SAE within one calendar day ie, immediately but no later than 24 hours of when he or she becomes aware of it).

If the electronic data capture system is not available, then the Investigator or other study site staff reports an SAE to the appropriate AstraZeneca representative by telephone.

The AstraZeneca representative will advise the Investigator/study site staff how to proceed.

The reference document for definition of expectedness/listedness is the Investigator's Brochure for benralizumab.

For further guidance on the definition of an SAE, see Appendix B.

8.3.8 Pregnancy

All pregnancies and outcomes of pregnancy should be reported to the AstraZeneca representative unless the pregnancy is discovered before the study participant has received any IP.

If a pregnancy is reported, the Investigator should inform the AstraZeneca representative within 24 hours of learning of the pregnancy.

Abnormal pregnancy outcomes (eg, spontaneous abortion, foetal death, stillbirth, congenital anomalies, and ectopic pregnancy) are considered SAEs.

8.3.8.1 Maternal Exposure

If a participant becomes pregnant during the course of the study, IP should be discontinued immediately.

Pregnancy itself is not regarded as an AE unless there is a suspicion that the IP under study may have interfered with the effectiveness of a contraceptive medication. Congenital anomalies/birth defects and spontaneous miscarriages should be reported and handled as SAEs. Elective abortions without complications should not be handled as AEs. The outcome of all pregnancies (spontaneous miscarriage, elective termination, ectopic pregnancy, normal birth or congenital anomaly/birth defect) should be followed-up and documented even if the participant was discontinued from the study. If any pregnancy occurs in the course of the study, then the Investigator or other site personnel informs the appropriate AstraZeneca representative within one day (ie, immediately but no later than 24 hours of when he or she becomes aware of it).

The designated AstraZeneca representative works with the Investigator to ensure that all relevant information is provided to the AstraZeneca Patient Safety data entry site within 1 or 5 calendar days for SAEs (Section 8.3.7) and within 30 days for all other pregnancies.

The same timelines apply when outcome information is available.

